The original study design was a randomized Phase II study of two separate timed sequential Busulfan/fludarabine conditioning regimens with 50 patients in each arm. The primary objective was to compare the Day 100 non-relapse mortality (NRM) rate between the arms. On March 4, 2014, the MDACC Data and Safety Monitoring Board (DSMB) met and approved the study team's request to stop the randomization for this study and continue the study as a single-arm study with increased accrual onto the higher dose arm. The total accrual was almost complete at that time, and there were no significant differences in NRM between the arms and virtually no chance of seeing a difference at the end of the trial (predictive probability =0.0003). Therefore, we present below the revised statistical considerations for this study halting the randomization and continuing the study with an increase of 100 additional patients (150 patients total) in the higher dose arm.

The revised primary objective will be to assess the NRM rate in the higher dose arm. Secondary objectives include assessing overall and progression-free survival, time to platelet and neutrophil engraftment, the cumulative incidence of acute and chronic GVHD, and correlative studies of cytokines at serial time points.

Safety Monitoring

We will use Bayesian monitoring rules to monitor the 100-day NRM rate in the high dose arm and stop the study if there is strong evidence at any time that this rate exceeds 10%. We choose 10% rather than 20% based on the low NRM rate found in the randomized portion of the trial. Formally, we will stop accrual to the high dose arm if at any time:

$$\Pr(\text{Day 100 NRM in high dose arm} > 0.10 \mid \text{Data}) > 0.98$$

We assume a Beta (0.2, 1.8) prior distribution for the probability of NRM corresponding to a 10% mean, and assume a constant rate of 0.10 for the standard of care. Stopping boundaries and operating characteristics were generated using the Department of Biostatistics' Multicenter Lean Desktop version V2.1.

Patients will be monitored in cohorts of size 10. The stopping boundaries for this rule are:

# Total Patients in high dose arm (cohorts of 10)	Stop the trial if there are this many or more NRM100 total in the high dose arm:
10	4-10
20	6-20
30	8-30
40	9-40
50	11-50
60	12-60
70	13-70
80	15-80
90	16-90
100	17-100
110	19-110
120	20-120
130	21-130
140	23-140
150	Always stop with 150 patients in high dose arm

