The operating characteristics of this rule are presented below. There is approximately a 6% chance of stopping the study early if the true Day 100 NRM rate in the high dose arm is 10%.

True NRM rate in high dose arm	Pr(early stop)	Sample Size (25th, 50th, 75th percentiles)		
		150	150	150
0.05	0.0014	150	150	150
0.10	0.0634	150	150	150
0.20	0.5172	60	130	150
0.30	0.9302	30	50	80
0.40	1.0000	10	20	30

Analysis Methods

Continuous data will be summarized using descriptive statistics (mean, standard deviation, median, inter-quartile range, range). Categorical data will be summarized using frequency counts and percentages.

The proportion of patients with NRM will be reported for each treatment arm, along with 95% Bayesian credible intervals. A sample size of 150 patients in the high dose arm will provide a confidence interval of (5.2%, 14.8%) for a 10% Day 100 NRM rate.

Overall survival and progression-free survival will be calculated from the time of transplant by the method of Kaplan and Meier. Cox proportional hazards regression analysis will be used to assess the association between these survival parameters and clinical and treatment covariates of interest.

The time to platelet and neutrophil engraftment will be calculated from the time of transplant and estimated by the Kaplan-Meier method. The cumulative incidence of acute and chronic GVHD with the competing risk of relapse will be estimated using the method of Gooley and the method of Fine and Gray will be used to model this incidence by disease and clinical characteristics of interest. Secondary analysis will also include analyzing NRM with these methods while taking into account the competing risk of deaths due to other causes within 100 days. Generalized linear mixed models will be used to assess the association between cytokines over time and treatment and other factors.

The change in busulfan PK between the first dose (day -13) and the third dose (day -6) will be compared using t test. Percentage of patients who achieve the targeted systemic busulfan exposure ($\pm 10\%$) based on first dose PK recommendation and overall population PK will be summarized using descriptive statistics. The PK analysis will be correlated with toxicity and efficacy.

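### Operating characteristics of the NRM stopping rule are printed against the wrong true rates: at 20% NRM the table says 52% early stopping, but the printed rule gives 93%

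*Combined protocol and SAP*

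**What the plan says.** Under Statistical Considerations, Safety Monitoring, accrual to the high dose arm stops if the posterior probability that Day 100 NRM exceeds 0.10 is above 0.98. On the prior the plan says "We assume a Beta (0.2, 1.8) prior distribution for the probability of NRM corresponding to a 10% mean". For the comparator it says "assume a constant rate of 0.10 for the standard of care". On timing: "Patients will be monitored in cohorts of size 10". The maximum is 150 patients, and stopping counts are printed for each look from 10 to 140.

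The table that follows is presented as the operating characteristics of this rule. Its columns are the true NRM rate, the probability of early stopping, and the 25th, 50th and 75th percentiles of sample size. The 0.05 and 0.10 rows give early-stop probabilities of 0.0014 and 0.0634, and the text repeats the latter as about 6%. The other three rows are:

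- "0.20 0.5172 60 130 150"
- "0.30 0.9302 30 50 80"
- "0.40 1.0000 10 20 30"

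**The concern.** A rule tuned to detect NRM above 10% with up to 150 patients should not miss a doubling to 20% about half the time. By the look at 140 patients, 28 events are expected at a 20% rate (140 × 0.20), against a boundary of 23. A stopping probability near one half is what would be expected at a rate only slightly above the threshold, so the row labels were suspect.

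Day 100 NRM is the primary endpoint, and this table is the plan's only statement of how well the rule protects against an excess. The Protocol Monitoring section also offers the rule as the reason for having no interim analysis schedule, and the DSMB entry is marked not applicable. The 20% row matters most, because the plan explains that it monitors against 10% in preference to 20%. A reader judging whether the rule is adequate, or reusing it in a later trial, would take the wrong sensitivity and the wrong expected sample size from the table.

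**Working it through.** **Inputs, all from Safety Monitoring.** Beta(0.2, 1.8) prior; threshold 0.10; cut-off 0.98; looks at n = 10, 20, …, 140; maximum 150; the printed boundaries.

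**Step 1: boundaries.** With x events in n patients the posterior is Beta(0.2 + x, 1.8 + n − x). The boundary is the smallest x for which Pr(p > 0.10) exceeds 0.98. At n = 10, x = 3 gives 0.9328 and x = 4 gives 0.9870, so the boundary is 4. At n = 140, x = 22 gives 0.9787 and x = 23 gives 0.9885, so the boundary is 23. Across all looks the result is 4, 6, 8, 9, 11, 12, 13, 15, 16, 17, 19, 20, 21, 23. This matches the printed list at all 14 looks.

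**Step 2: operating characteristics.** Let f(x) be the probability of having x events without having stopped. At each look, add a Binomial(10, p) count to f, move the probability at or above the boundary into the stopped total, and carry the rest forward. Early stopping is the stopped total after n = 140; trials that never cross run to 150. The percentiles are read from the cumulative stopping probabilities.

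| True NRM | Exact Pr(early stop) | Exact percentiles | Printed row with this result |
|---|---|---|---|
| 0.05 | 0.0014 | 150/150/150 | 0.05 (agrees) |
| 0.10 | 0.0634 | 150/150/150 | 0.10 (agrees) |
| 0.15 | 0.5172 | 60/130/150 | labelled 0.20 |
| 0.20 | 0.9302 | 30/50/90 | labelled 0.30 (prints 30/50/80) |
| 0.30 | 0.99997 | 10/20/30 | labelled 0.40 |
| 0.40 | 1.0000 | 10/10/20 | none |

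The first two rows reproduce the plan's own figures, so the method is the one behind the table. Solving in reverse for the rate that yields each printed probability gives 0.1500 for 0.5172 and 0.2000 for 0.9302.

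**Step 3: two checks that need no recursion.**

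- At p = 0.20, Pr(23 or more events in 140) = 0.879. A trial with that count has stopped by n = 140 at the latest, so early stopping is at least 0.879. The printed 0.5172 is impossible.
- At p = 0.40, Pr(4 or more events in 10) = 0.618. More than half of trials stop at the first look, so the median is 10. The printed median of 20 is impossible.

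**Step 4: other readings of the rule.** Keeping the 10% threshold and 0.98 cut-off, early stopping at a true 20% was 0.886 to 0.956 across a boundary one event higher, a later first look (20, 50 or 60), an added look at 150, and continuous monitoring. It was 0.80 with the maximum cut to 100. Cut-offs of 0.95, 0.975 and 0.99 gave 0.969, 0.946 and 0.888. Replacing the threshold with 0.20 gave 0.056. None gives 0.517.

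**The case against.** The error does not reach the rule. The prior, cut-off, boundaries and the 6% statement at 10% NRM are all right. The table understates stopping at 20% and 30%, so nobody is falsely reassured about those rates. The study has been closed to new entry since 08/02/2018, so a correction cannot alter accrual. All of this stands. It limits the harm to the record and to judgements or later designs that rely on the table, but it does not make the figures correct.

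The fit after relabelling is not perfect. At 0.20 the exact 75th percentile is 90, and the table prints 80. Cumulative stopping by n = 80 is 0.7471, just short of 0.75, so simulation or rounding in the source software could account for it; the plan does not say. This favours a rerun over relabelling alone.

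In the row labelled 0.40 the early-stop probability is not wrong, since 1.0000 is right at both 0.30 and 0.40. Only the percentiles show that the row belongs to 0.30. That the label 0.15 was skipped is likewise an inference from the fit. A stray unlabelled line of 150s appears in the extracted table, but there are five labels and five complete rows, so it does not explain the shift.

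Finally, 93% with a median of 50 describes the rule applied from the first patient. The Overview says accrual to the randomized design, 50 per arm, was almost complete when the rule was rewritten. The event count at that point is not given. Assuming 50 patients in the arm with 2, 3, 4 or 5 events, a 20% rate afterwards, and looks from n = 60, early stopping is 0.29, 0.39, 0.50 or 0.62. That is a fair caution against reading 93% as the protection given to the added patients. It does not rescue the table, which covers looks from n = 10 and matches from-the-start figures in its first two rows.

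**Conclusion.** The point holds. The rows labelled 0.20, 0.30 and 0.40 carry the results for true NRM rates of 0.15, 0.20 and 0.30.

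- **At 20%:** early stopping is printed as 0.5172 and should be 0.9302, a difference of 0.4130. The median sample size is printed as 130 and should be 50.
- **At 30%:** early stopping is printed as 0.9302 and should be 0.99997. The median is printed as 50 and should be 20.
- **At 40%:** the probability is right, but the percentiles should be 10/10/20.
- **At 15%:** this is where the rule stops about half the time (0.5172), and the table does not show it.

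The result assumes independent patients with a constant NRM rate, outcomes known at each look, and the rule applied from the first patient. The first two rows of the table reproduce under the same assumptions. The stopping boundaries are unaffected.

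**What to change.** Rerun the table from the printed rule and show true rates of 0.05, 0.10, 0.15, 0.20, 0.30 and 0.40. The early-stop probabilities should come out at 0.0014, 0.0634, 0.5172, 0.9302, 1.0000 and 1.0000, with the percentiles in the working table above. Relabelling the last three rows 0.15, 0.20 and 0.30 would also correct the probabilities, but it would leave the 75th percentile of 80 at 20% NRM unexplained against an exact 90.

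A note under the table should say that the figures apply to the rule from the first patient and are not conditional on the patients already treated. Any report or later design that cites the table should use the corrected values.

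The cost is one rerun and a table replacement. Boundaries, sample size, patients and procedures stay as they are.

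### Does it matter that the precision figure for Day 100 NRM is a confidence interval when the plan will report Bayesian credible intervals?

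*Combined protocol and SAP*

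**What the plan says.** All the relevant text is in the Statistical Considerations of the combined protocol and SAP.

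- **Overview**, on the aim: "The revised primary objective will be to assess the NRM rate in the higher dose arm". The size of that arm comes from "an increase of 100 additional patients (150 patients total) in the higher dose arm".
- **Safety Monitoring**, on the prior: "We assume a Beta (0.2, 1.8) prior distribution for the probability of NRM corresponding to a 10% mean". It is used to stop accrual if the posterior probability that NRM exceeds 0.10 is greater than 0.98. It is the only prior in the document.
- **Analysis Methods**, on reporting: "The proportion of patients with NRM will be reported for each treatment arm, along with 95% Bayesian credible intervals".
- **Analysis Methods**, next sentence, on precision: "A sample size of 150 patients in the high dose arm will provide a confidence interval of (5.2%, 14.8" (upper limit in per cent). The rate assumed there is 10%. No confidence level or method is named.

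**The concern.** Two neighbouring sentences on the primary endpoint speak different statistical languages. One commits to Bayesian credible intervals. The next gives the only precision figure for that endpoint and calls it a confidence interval. A reader who takes the second as an illustration of the first will find that the figure is not an exact credible interval under the plan's own prior.

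There is also a gap in specification. The prior appears under Safety Monitoring, for the stopping rule in the high dose arm. Nothing expressly carries it to the final report or to the lower dose arm, and the choice between equal-tailed and highest-density limits is not stated. If the interval drove a conclusion, leaving its prior and form open until the data were known would be a real weakness: two analysts could report different limits from the same data, and the more favourable pair could be chosen.

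**Working it through.** **Inputs.** n = 150 in the high dose arm (Overview). Rate 10%, so 0.10 × 150 = 15 events (Analysis Methods). Prior Beta(0.2, 1.8) (Safety Monitoring). The confidence level is not printed; 95% is assumed, and it reproduces the figure.

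**1. The plan's own figure.** The Wald interval is p ± 1.96 × √(p(1 − p)/n).

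- Standard error: √(0.10 × 0.90 / 150) = 0.02449.
- Half-width: 1.96 × 0.02449 = 0.0480.
- Limits: 0.10 ± 0.0480 = 5.2% and 14.8%.

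This matches both printed limits. Other common confidence intervals do not: Wilson gives 6.2% to 15.8%, Agresti-Coull 6.1% to 15.9%, Clopper-Pearson 5.7% to 16.0%, and Wald with continuity correction 4.9% to 15.1%.

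**2. Is Beta(0.2, 1.8) the prior really in use?** For n = 10, 20, …, 140, the smallest count x with Pr(NRM > 0.10) > 0.98 under Beta(0.2 + x, 1.8 + n − x) is 4, 6, 8, 9, 11, 12, 13, 15, 16, 17, 19, 20, 21, 23. All 14 printed stopping boundaries agree.

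**3. The credible interval under that prior.** The posterior is Beta(0.2 + 15, 1.8 + 135) = Beta(15.2, 136.8), with mean 15.2/152 = 10.0%.

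| Interval for 15/150 | Lower | Upper | Width (points) |
|---|---|---|---|
| Printed (Wald) | 5.2% | 14.8% | 9.6 |
| Equal-tailed, Beta(0.2, 1.8) | 5.8% | 15.2% | 9.5 |
| Highest-density, Beta(0.2, 1.8) | 5.5% | 14.8% | 9.4 |

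Against the printed figure, the equal-tailed limits are 0.6 points higher (lower) and 0.4 points higher (upper). The highest-density lower limit is 0.3 points higher, and its upper limit is the same to one decimal.

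**4. How much posterior probability the printed interval holds.** Under Beta(15.2, 136.8), 1.07% lies below 5.2% and 3.43% above 14.8%. So 100 − 1.07 − 3.43 = 95.5% lies inside. The tails are unequal, but the total is not short of 95%. A normal approximation to this posterior (mean 0.100, standard deviation 0.02425) gives 5.25% to 14.75%, which rounds to the printed limits.

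**5. How much the open choice of prior could matter.** The alternatives below are assumptions and do not appear in the plan. For 15/150, a uniform prior gives 6.2% to 15.9% equal-tailed and 5.9% to 15.5% highest-density; a Jeffreys prior gives 6.0% to 15.6% and 5.7% to 15.2%. Over all three priors and both forms, the lower limit runs from 5.5% to 6.2% and the upper from 14.8% to 15.9%, a spread of 0.7 and 1.1 points.

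**6. The smaller arm.** The original design had 50 patients per arm. For an assumed 2 events in 50, the equal-tailed interval is 0.6% to 11.1% with Beta(0.2, 1.8) and 1.2% to 13.5% with a uniform prior. The upper limit moves by 13.5 − 11.1 = 2.4 points.

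**The case for a change.** The strongest case for a change is that these two sentences are the whole estimation plan for the primary endpoint, that the mismatch between them is plain, and that repair would cost a sentence or two. An interval for a primary endpoint ought to be reproducible from the plan, and a prior given for one arm's stopping rule is not automatically the prior for a final report on both arms. Closure to new entry does not remove the point, because it concerns analysis and not accrual.

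Part of this stands. The link between the monitoring prior and the final interval is left to inference, the form of the interval is not named, and in a 50-patient arm with few events the prior has a visible effect.

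The rest is weaker than it looks. The printed figure is labelled a confidence interval and is right as one; planning precision by a normal approximation and reporting by another method is ordinary practice. The prior is stated for the NRM probability itself and has no competitor in the document, so carrying it over is the natural reading. The revised primary objective concerns the higher dose arm only, so the sensitivity in the smaller arm touches a descriptive comparison figure. Finally, the room for a choice after the data are seen is about one point at most in the primary arm, even with priors the plan never mentions, and no conclusion is tied to where the limits fall.

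**Conclusion.** The observation is accurate, but it does not call for a change. It is a small gap that an analyst fills sensibly, not an arithmetic error. Used with the plan's only prior, the declared method gives limits within 0.6 points of the printed ones and nearly the same width, so the figure is a fair guide to the precision of 150 patients.

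The primary objective is to estimate the rate; no test or success threshold rests on the final interval. The stopping boundaries rest on the stated prior and the 0.98 cut-off and reproduce without reference to this figure. Sample size and boundaries would be the same whichever interval were quoted.

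This rests on two assumptions: that the printed interval is at the 95% level, which its exact reproduction supports, and that the monitoring prior carries over to the final report, which the plan implies without saying so. If a uniform or Jeffreys prior were used instead, the limits for 15/150 would differ from the printed ones by about one point at most, and the conclusion would be the same. When the results are reported, naming the prior for each arm and the interval type would be good practice.

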Phase II Study of Timed Sequential Busulfan in Combination with Fludarabine in Allogeneic Stem Cell Transplantation
2011-0958

Core Protocol Information

Short Title:	Allogeneic Transplantation Using Timed Sequential Busulfan and Fludarabine Conditioning
Study Chairman:	[name]
Department:	Stem Cell Transplantation and Cellular Therapy
[contact]
Unit:	423
Full Title:	Phase II Study of Timed Sequential Busulfan in Combination with Fludarabine in Allogeneic Stem Cell Transplantation
Protocol Phase:	Phase II
Version Status:	Activated -- Closed to new patient entry as of 08/02/2018
Version:	23
Document Status:	Final

Abstract

Objectives:

Primary Objective:

This is a Phase II study which primary objective is to assess the day 100 non-relapse mortality rates of timed sequential busulfan and fludarabine conditioning regimen.

Secondary Objectives:

To evaluate efficacy of this therapy by studying the following endpoints:

- a. Overall Survival,
- b. Progression free survival,
- c. Neutrophil and Platelet engraftment, and
- d. Estimate acute and chronic GVHD.

Tertiary Objectives:

To study impact of timed sequential busulfan therapy on:

- a. Gene expression in tumor cells, and
- b. Cytokines (both in plasma and cells).
- c. The change in busulfan pharmacokinetics (PKs) between day -13 and day -6 dosing.

Rationale: (Be as concise as possible)

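### Engraftment is to be estimated by Kaplan-Meier, which censors deaths before engraftment and so overstates the proportion of patients who engraft

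*Combined protocol and SAP*

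**What the plan says.** The Abstract lists "Neutrophil and Platelet engraftment" among the secondary objectives that evaluate efficacy. The Overview under Statistical Considerations repeats it in a list that includes "time to platelet and neutrophil engraftment, the cumulative incidence of acute and chronic GVHD".

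The estimator is named under Analysis Methods: "The time to platelet and neutrophil engraftment will be calculated from the time of transplant and estimated by the Kaplan-Meier method". That sentence is the whole specification. No competing event is named, and no section says how a patient who dies without engrafting enters the analysis.

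The neighbouring sentences treat similar endpoints differently. For GVHD: "The cumulative incidence of acute and chronic GVHD with the competing risk of relapse will be estimated using the method of Gooley", with Fine and Gray regression for covariates. For NRM, a secondary analysis applies the same methods while "taking into account the competing risk of deaths due to other causes within 100 days".

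**The concern.** Death before engraftment is a competing event, not a loss to follow-up. Kaplan-Meier censoring assumes that the censored patient remains able to engraft later at the same rate as those still observed. For a dead patient this is false. The estimator takes that patient's share of probability and passes it to the survivors, so the death does not count as a failure to engraft.

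This matters here because the trial tests a conditioning regimen whose primary endpoint is early non-relapse death. Patients who die before count recovery are among the failures an engraftment endpoint should show. Following the plan as written, they would not lower the reported engraftment probability. The authors evidently recognised the problem for GVHD and NRM, but did not carry the method over to engraftment.

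**Working it through.** **Is there a plan figure to reproduce?** Not for engraftment: the documents state no expected rate, landmark day or precision for it. The figures taken from the plan are the sample size, "100 additional patients (150 patients total) in the higher dose arm", and the reference rate of early non-relapse death, 10% by day 100. As a check on these two, the Wald interval is 0.10 ± 1.96 × √(0.10 × 0.90 / 150) = 0.10 ± 0.048, or 5.2% to 14.8%. This agrees with the plan's statement that 150 patients "provide a confidence interval of (5.2%, 14.8%) for a 10% Day 100 NRM rate".

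**Formulas.** Let F(t) be the probability of engrafting by day t if nobody died, and S_D(t) the probability of being alive at day t. Take the two as independent.

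- With deaths censored, one minus Kaplan-Meier estimates F(t).
- The proportion who actually engraft by t is the cumulative incidence, CI(t) = ∫₀ᵗ S_D(u) dF(u).

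Since S_D(u) ≤ 1, CI(t) ≤ F(t). The inequality is strict once deaths occur before some of the engraftments.

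**Illustration 1: platelets by day 100.** Assumed, not in the documents: log-normal engraftment time with median 16 days and log SD 0.6; 5% never engraft; constant death hazard λ = −ln(1 − D)/100, where D is the proportion dead by day 100.

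F(100) = 0.95 × Φ(ln(100/16)/0.6) = 0.95 × Φ(3.05) = 94.9%, whatever D is. CI(100) follows by numerical integration.

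| D | 1 − Kaplan-Meier | Cumulative incidence | Excess (points) | Patients in 150 | Median, KM (days) | Median, CI (days) |
|---|---|---|---|---|---|---|
| 3% | 94.9% | 94.3% | 0.5 | 0.8 | 16.65 | 16.69 |
| 5% | 94.9% | 94.0% | 0.9 | 1.4 | 16.65 | 16.72 |
| 10% | 94.9% | 93.0% | 1.9 | 2.8 | 16.65 | 16.80 |

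Seen as failures, non-engraftment is reported as 5.1% when it is 5.7%, 6.0% or 7.0%. At D = 10% about a quarter of the failures disappear: 1.9/7.0 = 27%.

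**Illustration 2: a different shape, both cell lines.** Assumed: normal engraftment times, neutrophils with mean day 13 and SD 3, platelets with mean day 20 and SD 8; 5% never engraft. One minus Kaplan-Meier is 95.0% throughout.

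| D by day 100 | Neutrophil CI, day 28 | Platelet CI, day 60 |
|---|---|---|
| 5% | 94.4% | 94.0% |
| 10% | 93.7% | 93.0% |
| 20% | 92.3% | 90.8% |

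If the proportion never engrafting is varied from 0% to 10%, the excess at 10% death is 1.2 to 1.4 points for neutrophils and 1.9 to 2.1 for platelets. The 20% row uses the older NRM reference rate that the Safety Monitoring section replaced with 10%.

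**Counting check, which needs no assumed engraftment distribution.** Of 150 patients, 4 die before the first engraftment, 3 are alive without engraftment at the end, and 143 engraft. The observed proportion is 143/150 = 95.3%; Kaplan-Meier gives 143/146 = 97.9%. (If the 4 deaths are instead spread evenly over 28 days and the assumed neutrophil times apply, Kaplan-Meier averages about 97.0%.) If 8 die before the first engraftment and the other 142 all engraft, Kaplan-Meier gives 100% against 142/150 = 94.7%.

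**The case against.** **The planned quantity is a time, not a rate.** The plan speaks of time to engraftment and sets no landmark or target rate, while GVHD is explicitly a cumulative incidence. In the first illustration the median moves by only 0.04 to 0.15 day. The point about the median stands. But the Abstract lists engraftment itself as the objective, and a Kaplan-Meier curve of it will be read as the proportion engrafted.

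**Censoring at death is inferred.** The plan does not state it. If patients who die were kept in the risk set to the end of the window, one minus Kaplan-Meier would equal the cumulative incidence in the absence of other censoring. That is true, but it is not what the method does by default, and nothing in the plan asks for it.

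**The bias is small and early deaths are counted elsewhere.** The excess of 0.5 to 1.9 points lies inside the sampling error of a proportion near 94% with 150 patients: the 95% half-width at 94% is 1.96 × √(0.94 × 0.06/150) = 3.8 points. Non-relapse deaths are the primary endpoint and are monitored in cohorts of 10; all deaths count in overall survival. This limits the consequence. It does not excuse the estimator: sampling error falls either way, whereas this error always favours the regimen.

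**The GVHD sentence is an imperfect model.** It names relapse, not death, as the competing risk. This is correct. The estimator carries over, but the competing event for engraftment must be named in its own right.

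**Conclusion.** The concern holds. Following the named method would give an engraftment probability at or above the true one, and strictly above it whenever a patient dies unengrafted while others go on to engraft. If no such death occurs, the two estimators agree.

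The direction follows from censoring those deaths and needs no further assumption; the size does. With about 10% dead by day 100, the illustrations put the excess at roughly 1 to 2 points, less for neutrophils than for platelets. It would be larger if deaths cluster among patients with delayed recovery, because the illustrations take death and engraftment as independent. All engraftment times and failure rates used are assumptions.

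The effect is confined to a secondary endpoint. The primary NRM analysis, the stopping rule and the sample size do not change, and the median time barely moves. The plan should be corrected, but the trial's main conclusion does not depend on it.

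**What to change.** Replace the engraftment sentence in Analysis Methods with one stating that neutrophil and platelet engraftment, measured from transplant, will be estimated by cumulative incidence with death before engraftment as the competing event, using the estimator already named for GVHD. Name the competing event explicitly, and state how relapse or a second transplant before engraftment is handled. Report median time to engraftment separately, labelled as applying to engrafted patients only, so that it is not read as a measure of success.

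The cost is one or two sentences. No new data are needed, and neither sample size nor conduct changes. Accrual is closed, but this is an analysis change that can be applied to the data already collected.

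### Relapse is the only competing event named for GVHD, and engraftment uses Kaplan-Meier: deaths would by default be censored, which can push both proportions up

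*Combined protocol and SAP*

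**What the plan says.** The relevant text is in the combined protocol and SAP, Statistical Considerations, Analysis Methods.

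- **GVHD estimate:** "The cumulative incidence of acute and chronic GVHD with the competing risk of relapse will be estimated using the method of Gooley".
- **GVHD regression:** "the method of Fine and Gray will be used to model this incidence by disease and clinical characteristics of interest". The model takes over whatever competing-event definition the estimate uses.
- **Engraftment:** "The time to platelet and neutrophil engraftment will be calculated from the time of transplant and estimated by the Kaplan-Meier method". No competing event and no censoring rule is given.
- **NRM:** a secondary analysis uses the competing-risk methods while "taking into account the competing risk of deaths due to other causes within 100 days". This is the only place where death is named as a competing event.

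Both affected outcomes are secondary objectives. The Abstract lists "Neutrophil and Platelet engraftment" and acute and chronic GVHD. The Overview under Statistical Considerations lists "time to platelet and neutrophil engraftment, the cumulative incidence of acute and chronic GVHD".

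**The concern.** A patient who dies without GVHD can never develop it, and a patient who dies before engrafting can never engraft. A cumulative incidence estimator handles this only if death is on its list of competing events; naming the method does not supply the list. The list given here is relapse. Kaplan-Meier has no place for a competing event, so its default is to censor the death. That the deaths will be censored is an inference from the methods as written. The plan does not say so in words.

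Deaths after relapse are already removed by the relapse event, so the GVHD gap is relapse-free death. That belongs to the trial's own primary endpoint, so such deaths are expected. The NRM monitoring rule works with a 10% day-100 reference rate.

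The study is now single-arm. The GVHD and engraftment percentages are descriptive, and readers are likely to set them beside those of other regimens. A systematic upward shift does not show in a confidence interval. The incomplete event list would also carry into the Fine and Gray models.

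**Working it through.** **Inputs from the documents.** 150 patients in the high-dose arm (Overview: "continuing the study with an increase of 100 additional patients (150 patients total) in the higher dose arm"). A 10% day-100 NRM reference (Safety Monitoring: "assume a constant rate of 0.10 for the standard of care"). The 10% is only an upper guide to the share dying first by day 100, because some of those patients will already have had GVHD and most may have engrafted. The documents give no GVHD, relapse-first, death-first or engraftment rate, so every such rate below is an assumption.

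**The plan's own figure.** The plan states no figure for GVHD or engraftment. Its only precision statement is an interval of 5.2% to 14.8% for a 10% NRM rate. It reproduces: 1.96 × √(0.10 × 0.90 / 150) = 0.048, so 10% ± 4.8 points. The same formula gives 95% sampling half-widths of 7.8 points at 40%, 4.8 at 90% and 3.5 at 95%.

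**Direction.** With all events counted, GVHD incidence accumulates in proportion to exp(−Λg − Λr − Λd), where the Λ are the cumulative hazards of GVHD, relapse and death. With death censored the weight is exp(−Λg − Λr), which is never smaller. The estimate therefore cannot fall, and it rises whenever deaths come before later GVHD events. The same holds for 1-KM on engraftment.

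**GVHD size, constant hazards.** Let G, R and D be the true proportions with GVHD first, relapse first and death first. Put S = G + R + D, L = −ln(1 − S), g = L·G/S and r = L·R/S. With death censored the estimate is g/(g + r) × [1 − exp(−(g + r))].

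Example: G = 0.40, R = 0.25, D = 0.05. S = 0.70, L = 1.204, g = 0.688, r = 0.430. The estimate is 0.688/1.118 × (1 − exp(−1.118)) = 0.414.

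| Outcome | True | Relapse first | Die first | Reads |
|---|---|---|---|---|
| Chronic GVHD | 40% | 25% | 2% | 40.5% |
| Chronic GVHD | 40% | 25% | 5% | 41.4% |
| Chronic GVHD | 40% | 25% | 10% | 43.0% |
| Acute GVHD | 40% | 5% | 5% | 41.3% |

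**Engraftment size, constant hazards.** Let E be the true proportion engrafting, S = E + D and L = −ln(1 − S). Then 1-KM = 1 − exp(−L·E/S).

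Example: E = 0.90, D = 0.05. L = 2.996, L·E/S = 2.838, and 1-KM = 0.941.

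| True engraftment | Die first | 1-KM reads |
|---|---|---|
| 90% | 1% | 90.8% |
| 90% | 2% | 91.5% |
| 90% | 5% | 94.1% |
| 95% | 1% | 95.9% |
| 95% | 3% | 97.7% |

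**Bounds over any timing of deaths.** The lower bound is the true value, reached when all deaths follow the last event. The upper bounds need no hazard assumption:

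- Chronic GVHD, with relapses first, then deaths, then GVHD: (1 − R)·G/(1 − R − D). This is 0.75 × 0.40/0.70 = 42.9% for 5% dying first, and 0.75 × 0.40/0.65 = 46.2% for 10%.
- Engraftment, with deaths first: E/(1 − D). This is 0.90/0.95 = 94.7% and 0.95/0.97 = 97.9%.
- If every survivor engrafts, 1-KM reaches 100% however many died first.

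**Median time to engraftment.** The Kaplan-Meier median is ln 2/(L·E/S); the cumulative incidence median is −ln(1 − 0.5·S/E)/L. As a fraction of the horizon they are 0.244 and 0.250 (90% engrafting, 5% dying first), and 0.183 and 0.185 (95%, 3%).

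**Simulation check.** 1,000 trials of 150 patients were simulated with assumed daily hazards of 0.0055 for GVHD, 0.0015 for relapse and −ln(0.9)/100 for death. Mean day-100 GVHD incidence was 37.8% with relapse and death competing and 39.6% with death censored.

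**The case against.** The strongest reply has four parts.

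1. **Censoring of deaths is inferred.** The plan names relapse without saying that nothing else competes. If the analyst counts death as competing, or keeps patients who died in the risk set as never engrafted, the bias disappears. This is true, but the plan requires neither. A one-event list is most naturally read literally, and the NRM sentence that follows shows that the authors name death as competing when they mean it.

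2. **The engraftment endpoint is a time, and no proportion from 1-KM is promised.** A crude percentage with deaths in the denominator would also fit the plan's general rule for categorical data. This stands as a limit: the engraftment bias applies only to a proportion read from the curve, and the median is almost untouched. The Abstract, however, lists engraftment itself as an endpoint, so a reported Kaplan-Meier proportion cannot be excluded.

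3. **The shift is small, and may be nil if deaths come late.** This stands for GVHD: 0.5 to 3.0 points in the chronic GVHD examples, against a 7.8-point half-width. For engraftment at a true 90%, 1% to 2% dying first moves the figure by only 0.8 to 1.5 points. The larger engraftment shifts need 3% to 5% dying before engraftment. That may be high, since 10% is the NRM reference for all 100 days.

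4. **No test, threshold or decision hangs on these endpoints, and no comparison with other regimens is planned.** This also stands, and it limits the consequence to the reported percentages and the GVHD regression models. No size has been worked out for the effect on those models.

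**Conclusion.** The concern holds. Followed as written, the methods censor relapse-free death in the GVHD analyses and death before engraftment in the Kaplan-Meier analysis. The resulting proportions cannot be too low on this account, and are too high when deaths precede later events.

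Under the assumed rates the GVHD shift is well inside sampling error. The engraftment shift, if a proportion is read from 1-KM, approaches sampling error at the higher assumed death rates: 4.1 points against a half-width of 4.8 (true 90%, 5% dying first), and 2.7 calculated from unrounded values against 3.5 (true 95%, 3% dying first). These sizes rest on assumed rates and, apart from the bounds, on constant hazards; the direction rests only on the deaths being censored. The primary day-100 NRM proportion and the stopping rule are not affected.

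**What to change.** In Analysis Methods:

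- State that death without GVHD is a competing event, alongside relapse if relapse is kept, in both the Gooley estimate and the Fine and Gray models for acute and chronic GVHD.
- Estimate neutrophil and platelet engraftment by cumulative incidence, with death before engraftment as the competing event.

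The cost is a few words of analysis text and minor recoding. Cumulative incidence is already in the plan, and dates of death are already needed for overall survival. The reported GVHD and engraftment proportions will be slightly lower.
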